Study Objectives	 Primary objective: To assess the anti-tumor activity of Tenalisib as determined by the objective response rate (ORR) and duration of response (DoR) Secondary objectives: 		
	 To characterize safety and tolerability of Tenalisib. To assess progression free survival (PFS) 		
End points	 Efficacy: Overall response rate (ORR): ORR is defined as sum of complete response (CR) and partial response (PR) rates as defined by iwCLL guideline for CLL (Hallek et al. 2018). Duration of response (DoR): DoR is defined as the interval from the first documentation of CR/PR to first documentation of definitive disease progression or death from any cause. Progression-free survival (PFS): PFS is defined as the interval from first dose to first documentation of definitive disease progression or death from any cause. 		
	Safety: • Adverse Event (AE), Grade 3/4 AEs, Serious Adverse Event (SAE).		
Study Design and procedure	The trial is a Phase II, open label, Simon's two stage study design to evaluate the efficacy and safety of Tenalisib in 61 patients with CLL who have relapsed or are refractory after at least one prior therapy. In stage 1, 20 patients will be enrolled. If eight or fewer responders are observed at this stage, the study will be terminated. Else, 41 additional patients will be enrolled into stage 2. The study treatment Tenalisib (800 mg BID) will be administered orally in 28-		
	days of cycle over a period of 7 months (C1D1 to C8D1) in absence of definitive disease progression or unacceptable toxicity. The study will end when all ongoing subjects have reached their third tumor assessment on Cycle 8/Day 1 (C8D1) or have discontinued from the study for any reason, whichever is earlier. At the end of the study, all ongoing patients with no evident disease progression will be given an opportunity to enroll in an open-label compassionate medication use study [Protocol:RP6530-1803; NCT03711604] and will be followed up. The detailed study procedure is presented in Study assessment and Treatment schedule (Table 1). Anti-infective prophylaxis (e.g.		

CONFIDENTIAL Page 5 of 61

Version: 1.0, Dated 12 September 2019

	for herpes simplex virus (HSV), pneumocyctis Jirovecii pneumonia (PJP), hepatitis B virus (HBV), cytomegalovirus (CMV) are recommeded and will be	
	given at the discretion of study investigator. All safety laboratory assessments,	
	electrocardiogram (ECG) and radiological assessments (e.g. CT) will be	
	performed at the respective sites.	
Number of	Approximately 61 patients with relapsed/refractory CLL will be enrolled.	
patients		
Eligibility	Patients must meet all the following inclusion criteria to be eligible for	
Criteria	participation in this study:	
	1. Patients with diagnosis of B-cell CLL as confirmed by histopathology or flow cytometry.	
	 Disease status defined as refractory to or relapsed after at least one prior 	
	therapy.	
	3. Presence of measurable lymphadenopathy, defined as the presence of ≥ 1	
	nodal lesion that measures ≥ 1.5 cm in the longest diameter (LD) as	
	assessed by computed tomography (CT).	
	4. ECOG performance status ≤ 2 .	
	5. Male or female ≥ 18 years of age.	
	6. Life expectancy of at least 3 months.	
	7. Adequate bone marrow (BM), liver, and renal function as assessed by the	
	following laboratory requirements conducted within 14 calendar days	
	before starting study treatment.	
	a. Adequate bone marrow function.I. Haemoglobin ≥ 9 g/dl	
	II. Absolute neutrophil count (ANC) $\geq 1 \times 10^{9}$ L	
	III. Platelets $\geq 50 \times 10^{\circ}9/L$	
	Patients with hemoglobin, neutrophil and platelet counts below the	
	above specified values will be eligible if it is due to tumor	
	dissemination or infiltration to bone marrow and as per physician's	
	discretion. Hemoglobin and platelet requirements should not be met by	
	use of recent transfusion or growth factor support (G-CSF or	
	erythropoietin) within 3 weeks prior to assessment.	
	b. Adequate liver function.	
	I. Total bilirubin ≤1.5 times the upper limit of normal (ULN)	
	II. ALT and AST should be ≤ 3 x ULN. ALT and AST ≤ 5 x ULN if known liver involvement.	
	c. Adequate renal function: Calculated creatinine clearance ≥ 50 mL/min	
	(as calculated by the Cockcroft-Gault method) or Creatinine \(\leq 1.5\)	
	mg/dl.	
	8. Ability to swallow and retain oral medication.	
	9. Female patients who are not of child-bearing potential, and female patients	
	of child-bearing potential should have a negative serum pregnancy test	
	within 3 days prior to Cycle 1 Day 1 (C1D1). Female patients of child-	
	bearing potential must consent to use a medically acceptable method of	
	contraception as defined in $Appendix A$, throughout the study period and	
	for 30 days after the last dose of study drug.	

CONFIDENTIAL Page 6 of 61

Version: 1.0, Dated 12 September 2019

10. Male patients willing to use adequate contraceptive measures throughout the study period and for 12 weeks after the last dose of Tenalisib. 11. Willingness and ability to comply with trial and follow-up procedures and give written informed consent. 1. Patient with Richter's (large cell) transformation, or prolymphocytic **Exclusion criteria** leukemia (PLL) transformation. 2. Patients receiving any cancer therapy (i.e., chemotherapy, radiation therapy, immunotherapy and biologic therapy) or any cancer investigational drug within 3 weeks (21 days) or 5 half-lives (whichever is shorter) prior to C1D1. 3. Prior exposure to drug that specifically inhibits PI3K (e.g. idelalisib, copanlisib, duvelisib, umbralisib) 4. Patient with autologous / allogeneic stem cell transplant (ASCT/Allo-SCT) receiving treatment for active graft versus-host disease (GVHD). 5. Evidence of ongoing severe systemic bacterial, fungal or viral infection as assessed by the investigator. 6. Central nervous system (CNS) involvement of leukemia or lymphoma 7. Ongoing immunosuppressive therapy including systemic corticosteroids except as allowed per concomitant medication (Section 5.2). 8. Known history of severe liver injury including drug-induced liver injury (e.g. alcoholic liver disease, primary biliary cirrhosis, ongoing extrahepatic obstruction caused by stones, cirrhosis of the liver or portal hypertension) as judged by investigator; 9. Any severe and/or uncontrolled medical conditions or other conditions that could affect patient participation in the study, as judged by investigator, such as: Symptomatic or history of documented congestive heart failure (New York heart association (NYHA) functional classification III-IV) b. Myocardial infarction within 6 months of C1D1 c. QTcF >470 msec. d. Angina not well-controlled by medication. e. Poorly controlled atherosclerotic vascular disease (e.g. cerebrovascular accident, transient ischemic attack, angioplasty, cardiac/vascular stenting). 10. Patient treated for other malignancy in last 3 years of study enrollment except for adequately treated basal, squamous cell carcinoma or nonmelanomatous skin cancer, carcinoma in situ of the cervix, superficial bladder cancer not treated with intravesical chemotherapy or BCG within 6 months; and localized prostate cancer with PSA <1.0 mg/dL within 4 weeks of C1D1. 11. Women who are pregnant or lactating. 12. Known seropositive requiring anti-viral therapy human immunodeficiency virus (HIV) infection. 13. Known seropositive requiring anti-viral therapy for hepatitis B virus (HBV) infection OR evidence of active hepatitis B infection as defined by detectable viral load if the antibody tests are positive. [Note: Subject with

CONFIDENTIAL Page 7 of 61 Protocol No: RP6530-1901 Version: 1.0, Dated 12 September 2019

a positive HBcAb with an undetectable/negative hepatitis B DNA test (e.g., polymerase chain reaction [PCR] test) can be enrolled]. 14. Known seropositive requiring anti-viral therapy for hepatitis c virus (HCV) infection OR patients with positive hepatitis C virus Ab with detectable Subject with a positive HCV load. [Note: undetectable/negative hepatitis C RNA test (e.g., PCR) can be enrolled]. 15. Known seropositive requiring anti-viral therapy for active CMV infection (Note: A serology positive CMV subject with negative CMV PCR test will be enrolled). 16. Unresolved NCI-CTCAE grade 2 and above toxicity (except as mentioned in adequate organ function (Refer inclusion criteria #7) attributed to any prior therapy/procedure excluding alopecia. 17. Inability or unwillingness to comply with study and/or follow-up procedures outlined in the protocol; 18. Concurrent condition that in the investigator's opinion would jeopardize compliance with the protocol. Concomitant Antimicrobial and/or anti-viral prophylaxis should be used according to medication local standard practice; PJP and herpes zoster prophylaxis is strongly recommended. CMV carriers will be monitored per institutional guidelines and/or will be given anti-CMV therapy (e.g., ganciclovir, valganciclovir). Similarly, chronic carriers of HBV should receive prophylactic anti-viral therapy. G-CSF and other hematopoietic growth factors may be used for the management of acute toxicity (such as febrile neutropenia) when clinically indicated. Transfusions (blood/platelets) may be given, based on standard criteria and clinical judgment. No routine prophylactic anti-emetics or pre-medications should be given outside of protocol requirements. However, these medications may be administered for the treatment of symptoms. Patient may receive prophylactic allopurinol, in case the risk of tumor lysis syndrome. Low doses of steroids are allowed if it administered at dose ≤ 20 mg per day of prednisone or equivalent. The dose should be stabilized for at least 1 week or 5 half-lives (whichever is shorter) prior to C1D1. Patients are permitted to use of topical, ocular, intra-articular, intranasal, and inhaled corticosteroids (with minimal systemic absorption). Inactivated seasonal influenza vaccine can be given to subjects before treatment and while on therapy without restriction. If concomitant treatment of drugs metabolized by CYP3A4/CYP2C9 enzymes are clinically warranted, careful observation of the patient is advised. Low molecular weight heparin (LMWH), Dabigatran or Edoxaban is acceptable for prophylaxis and/or treatment of venous thrombosis. The following treatments are prohibited while on the clinical trial: **Prohibited** • Any other anti-leukemia/lymphoma therapy medication

CONFIDENTIAL Page 8 of 61 Protocol No: RP6530-1901 Version: 1.0, Dated 12 September 2019

version: 1.0, Dated 12 Se	ptember 2019
	 Herbal medications. Patients should stop using herbal medications at least 7 days prior to C1D1. Strong inhibitors or inducers of CYP3A4. Patients should stop using these medications at least 7 days or 5 half-lives (whichever is shorter) prior to C1D1. Strong inhibitors or inducers of CYP2C9. Patients should stop using these medications at least 7 days or 5 half-lives (whichever is shorter) prior to C1D1. Substrates of CYP3A4 enzyme with a narrow therapeutic range. Patients should stop using these medications at least 7 days or 5 half-lives (whichever is shorter) prior to C1D1. Use of heparin, warfarin, apixaban or rivaroxaban for prophylaxis and/or treatment of venous thrombosis is prohibited. These drugs should be stopped at least 7 days or 5 half-lives (whichever is shorter) prior to C1D1. Live attenuated vaccine (e.g. Flu vaccine, pneumovax, varicella) Steroids > 20 mg unless it is required for management of toxicity (e.g., transaminitis) during the study.
Estimated Study	Approximately 10-12 months for patient accrual plus 7.5 months of treatment
duration	and follow up. Estimated clinical duration is about 20 months.
Response assessment	Efficacy will be evaluated by CT scan at C3D1±7 days, C5D1±7 days and C8D1±7 days or at End of the treatment (EOT) visit. The determination of response and progression will be based on iwCLL guidelines for diagnosis and treatment of CLL (Hallek et al. 2018). Unilateral bone marrow aspiration and/or biopsy will be performed at investigator discretion in patients for whom assessment of extent of CLL involvement and bone marrow cellularity is important in determining eligibility. However, bone marrow biopsy should be done to confirm potential CR. Radiographic and clinical tumor response as evaluated and confirmed by the site investigator (defined as PI-confirmed response) will be considered for
Cample des	analyses of ORR and other efficacy endpoints.
Sample size	The sample size is derived based on Simon's two stage design to achieve 90% power at alpha of 0.05 for the null hypothesis of $ORR \le 40\%$, assuming 60% response rate. Up to 61 patients will be enrolled. In stage 1, 20 patients will be enrolled. If eight or fewer responders are observed in this stage, the study will be terminated without rejecting the null hypothesis. Else, 41 additional patients will be enrolled into stage 2. If 31 or more responders are observed in the study, the null hypothesis of $ORR \le 40\%$ will be rejected.
Statistical Analysis	Statistical methods to analyze efficacy and safety will be described in statistical analysis plan (SAP). These methods may be revised and updated due to reasons such as regulatory requirements or need for further clarifications. The final analysis plan will be documented in a formal SAP that will be

CONFIDENTIAL Page 9 of 61

Protocol No: RP6530-1901 Rhizen Pharmaceuticals S.A.

Version: 1.0, Dated 12 September 2019

finalized before database lock. The SAP will include details on how variables will be derived, how missing data will be handled, and how data will be presented as well as the details on statistical methods to be used for safety and efficacy analyses. The final clinical study report will discuss deviations from the SAP, if any.

CONFIDENTIAL Page 10 of 61

Protocol No: RP6530-1901 Version: 1.0, Dated 12 September 2019

GENERAL INFORMATION			
SPONSOR			
SPONSOR'S REPRESENTATIVE			
SPONSOR'S MEDICAL EXPERT			
STATISTICIAN			

CONFIDENTIAL Page 11 of 61

Version: 1.0, Dated 12 September 2019

List of Abbreviations

ΑE Adverse Event ALP Alkaline Phosphatase Alanine aminotransferase ALT (SGOT) ANC Absolute Neutrophil Count

aPTT Activated Partial Thromboplastin Time

Allo-SCT Allogeneic Hematopoietic Stem Cell Transplantation Autologous Hematopoietic Stem Cell Transplantation Auto-SCT

AST (SGPT) Aspartate aminotransferase

AUC Area Under the plasma-concentration time curve

BID Twice Daily

β-HCG β-human chorionic gonadotropin Peak Drug Concentration C_{max} Complete Blood Count **CBC** Code of Federal Regulation **CFR**

Cytomegalovirus **CMV**

Chronic Lymphocytic Leukemia CLL Central Nervous System CNS CR Complete Response CRF Case Report Form CrCl Creatinine Clearance

Computed Tomography CT**CTCAE** Common Terminology Criteria for Adverse Events

CTCL Cutaneous T cell Lymphoma Dose Limiting Toxicity DLT **Duration of Response** DoR Data Review Committee DRC Deep Vein Thrombosis **DVT** Electrocardiogram **ECG**

Electronic Case Report Form eCRF

Eastern Cooperative Oncology Group Performance Status ECOG PS

EOS End of Study **EOT End of Treatment**

FDA Food and Drug Administration

FL Follicular lymphoma

Follicular Stimulating Hormone **FSH**

GCP **Good Clinical Practices**

Gamma Glutamyl Transpeptidase **GGT** Granulocyte Colony-Stimulating Factor G-CSF

Hemoglobin Hb **HBV** Hepatitis B Virus Hepatitis C Virus **HCV** HDL

High-Density Lipoprotein

Head, Eyes, Ears, Nose and Throat **HEENT**

Health Insurance Portability and Accountability Act **HIPAA**

Human Immune Deficiency Virus HIV

Investigator brochure IBInformed Consent Form **ICF**

ICH International Conference on Harmonization

Independent ethics committee IEC IRB/IEC Institutional Review Board **IWCLL** International Workshop on CLL

Intrauterine Device IUD **IUS** Intrauterine System LDH Lactate Dehydrogenase

CONFIDENTIAL Page 12 of 61

Version: 1.0, Dated 12 September 2019

LDL Low-Density Lipoprotein LLN Lower Limit of Normal

LMWH Low Molecular Weight Heparin

MedDRA Medical Dictionary for Regulatory Activities

mITT Modified Intent-to-Treat
MTD Maximum Tolerated Dose
NCI National Cancer Institute

NOAEL No-Observed-Adverse Effect Level NYHA New York Heart Association ORR Objective Response Rate

pAKT PhosphoAKT

PJP Pneumocystis *Jirovecii* Pneumonia

PD Progressive disease
PFS Progression-Free Survival
PI Principle Investigator
PI3K Phosphoinositide-3-Kinase

PK Pharmacokinetics
PP Per-Protocol
PR Partial Response
QA Quality Assurance
QTcF QTc Fredericia

SAE Serious Adverse Events
SAP Statistical Analysis Plan
SAS Statistical Analysis Software

SD Stable Disease

SDV Source Document Verification SOP Standard Operating Procedures SUV Standardized Uptake Value

t_{1/2} Plasma Half Life

 t_{max} Time to maximum plasma concentration TEAE Treatment-Emergent Adverse Event

TG Triglyceride TID Thrice Daily

TSH Thyroid Stimulating Hormone
ULN Upper Limit of Normal
USP United States Pharmacopeia

UV Ultra-violet
WBC White Blood Cells

WHO World Health Organization

CONFIDENTIAL Page 13 of 61

Version: 1.0, Dated 12 September 2019

TABLE OF CONTENTS

1	Back	kground Information	18
	1.1	Tenalisib (RP6530)	18
	1.2	Summary of pre-clinical evaluation	18
	1.3	Summary of clinical evaluation	18
	1.4	Study Rationale	19

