3.5.5 Precautions and risks associated with the Investigational Product

- Monitoring of liver enzymes and levels of TSH, T3, and T4 in subjects receiving Tenalisib is recommended based on target organ toxicity. Patients should be monitored for increased ALT/AST, skin rash, neutropenia as these events are reported with Tenalisib. Monitor patients for signs and symptoms of these events and interrupt Tenalisib for Grade 3 or higher event. In addition, monitor patients for diarrhea/ colitis and pneumonitis as these events are reported with agents of PI3K inhibitor class.
- Patients with CLL are at increased risk for infection (including sepsis and/or opportunistic infection with Pneumocystis *jirovecii* or Herpesviridae (herpes simplex virus, varicella-zoster virus, CMV, Epstein-Barr virus)) because of compromised immune function, which might be related to the disease itself and/or to the consequences of therapy. Therefore, monitor patients for signs and symptoms of infection and interrupt Tenalisib for Grade 3 or higher infection. The severity of infections should be quantified as minor (requiring either oral antimicrobial therapy or symptomatic care alone), major (requiring hospitalization and systemic antimicrobial therapy), or fatal (death as a result of the infection).
- Tenalisib shows moderate to high inhibition of CYP3A4 enzymes. Therefore, concomitant administration of Tenalisib with CYP3A4 substrates (e.g. calcium channel blockers, warfarin, carbamazepine, macrolide antibiotics, lovastatin, simvastatin, terfenadine) may reduce clearance of these drugs increasing the risk of adverse events. Similarly, as Tenalisib is inhibited by CYP3A4 and CYP2C9, there is possibility of drug interaction with inhibitors or inducers of CYP3A4 and CYP2C9. If concomitant treatment of these drugs is clinically warranted, careful observation of the patient is advised. Raised INR has been reported with concomitant warfarin administration. Therefore, use of heparin or warfarin to be avoided. Low molecular weight heparin (LMWH), Dabigatran or Edoxaban is advised for prophylaxis and treatment of venous thrombosis.
- Strong inhibitor or inducers should be avoided as directed in Section 5.3 on prohibited medication. Please refer to the recent Investigator Brochure for additional safety
- In absence of reproductive toxicity and genotoxicity data, the study participants should be advised to follow post treatment contraceptive measures.

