4 SELECTION AND WITHDRAWAL OF SUBJECTS

4.1 Inclusion Criteria

Patients must meet all the following inclusion criteria to be eligible for participation in this study:

- 1. Patients with diagnosis of B-cell CLL as confirmed by histopathology or flow cytometry.
- 2. Disease status defined as refractory to or relapsed after at least one prior therapy.
- 3. Presence of measurable lymphadenopathy, defined as the presence of ≥ 1 nodal lesion that measures ≥ 1.5 cm in the longest diameter (LD) as assessed by computed tomography (CT).
- 4. ECOG performance status ≤ 2 .
- 5. Male or female ≥ 18 years of age.
- 6. Life expectancy of at least 3 months.
- 7. Adequate bone marrow (BM), liver, and renal function as assessed by the following laboratory requirements conducted within 14 calendar days before starting study treatment.
 - a. Adequate bone marrow function:
 - I. Haemoglobin ≥ 9 g/dl
 - II. Absolute neutrophil count (ANC) $\geq 1 \times 10^{9}/L$
 - III. Platelets $>50 \times 10^{9}/L$

Patients with hemoglobin, neutrophil and platelet counts below the above specified values will be eligible if it is due to tumor dissemination or infiltration to bone marrow and as per physician's discretion. Hemoglobin and platelet requirements should not be met by use of recent transfusion or growth factor support (G-CSF or erythropoietin) within 3 weeks prior to assessment.

- b. Adequate liver function:
 - I. Total bilirubin ≤ 1.5 times the upper limit of normal (ULN)
 - II. ALT and AST should be ≤ 3 x ULN. ALT and AST ≤ 5 x ULN if known liver involvement.
- c. Adequate renal function: Calculated creatinine clearance ≥ 50 mL/min (as calculated by the Cockcroft-Gault method) or Creatinine ≤ 1.5 mg/dl.
- 8. Ability to swallow and retain oral medication.
- 9. Female patients who are not of child-bearing potential, and female patients of child-bearing potential should have a negative serum pregnancy test within 3 days prior to Cycle 1 Day 1 (C1D1). Female patients of child-bearing potential must consent to use a medically acceptable method of contraception as defined in *Appendix A*, throughout the study period and for 30 days after the last dose of study drug.

Protocol No: RP6530-1901 Version: 1.0, Dated 12 September 2019

- 10. Male patients willing to use adequate contraceptive measures throughout the study period and for 12 weeks after the last dose of Tenalisib.

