7.2 Adverse Event/Serious Adverse Event Causality Assessment

Causality is assessing the relationship of adverse event to the study drug. For this study, the causality assessment will be categorized as related and not related.

- **Related:** All toxicities should be considered related to Tenalisib unless there is a clear alternative explanation.
- **Not related:** If there is no temporal association, or another etiology has been identified as the cause, or the study drug cannot be implicated based upon the current information.

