7.4 Severity of Adverse events

Severity of adverse events will be assessed according to National Cancer Institute (NCI)- CTCAE v5.0 with exceptions for platelet, hemoglobin and ANC that are recommended by iwCLL guidelines for the CLL (see below).

Grade*	Decrease in platelet† or Hb‡ (nadir) from baseline, %	Absolute neutrophil count (nadir)§ x 10 ⁹ /L	
0	No change to 10	≥2	
1	11-24	\geq 1.5 and \leq 2	
2	25-49	$\geq 1 \text{ and } < 1.5$	

CONFIDENTIAL Page 40 of 61

Version: 1.0, Dated 12 September 2019

3	50-74	≥0.5 and <1	
4	≥ 75	< 0.5	

^{*} Grades: 1-mild; 2-moderate; 3-severe; 4-life-threatening; 5-fatal. Death occurring as a result of toxicity at any level of decrease from baseline will be recorded as grade 5.

§ If the absolute neutrophil count (ANC) reaches $<1\times10^9/L$, it should be judged to be grade 3 toxicity. Other decreases in the white blood cell count or in circulating granulocytes are not to be considered because a decrease in the white blood cell count is a desired therapeutic end point. A gradual decrease in granulocytes is not a reliable index in CLL for stepwise grading of toxicity. If the ANC is $<1\times10^9/L$ before therapy, the patient is not evaluable for toxicity referable to the ANC. The use of G-CSF is irrelevant for the grading of toxicity but should be documented.

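### Inclusion 7a names G-CSF in its bar on recent support but leaves the ANC limit out of that bar, so the neutrophil criterion can be met on G-CSF

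*Protocol*

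**What the plan says.** Inclusion 7a appears in the protocol synopsis and in section 4.1, with the same wording on this point. It has three parts:

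- Limits for hemoglobin, ANC and platelets. The ANC limit is at least 1 x 10^9/L.
- A waiver that names all three counts. Values below the limits are accepted, at the physician's discretion, when the cause is disease in the marrow.
- A bar on support, which opens in the synopsis with "Hemoglobin and platelet requirements should not be met by" and reads in section 4.1: "Hemoglobin and platelet requirements should not be met by use of recent transfusion or growth factor support (G-CSF or erythropoietin) within 3 weeks" before the assessment. This sentence names two counts, not three.

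Pre-therapy ANC matters later in the plan. Under section 7.4, if ANC is below 1 x 10^9/L before therapy, "the patient is not evaluable for toxicity referable to the ANC". The same footnote says "The use of G-CSF is irrelevant for the grading of toxicity but should be documented". Section 7.2 sets the causality default: "All toxicities should be considered related to Tenalisib unless there is a clear alternative explanation". Section 3.5.5 lists neutropenia among the events already seen with the drug: "Patients should be monitored for increased ALT/AST, skin rash, neutropenia as these events are reported with Tenalisib".

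**The concern.** G-CSF is the granulocyte factor, and sections 5.2 and 7.7 (Table 4) connect growth-factor support with neutropenia. The bar therefore applies G-CSF to the two counts it is not given for and is silent on the one it raises. Two things are at stake.

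- **Safety at entry.** An ANC reached on support does not show the adequate marrow function that 7a is meant to establish. Section 3.5.5 lists neutropenia as a reported event, and section 1.4.1 calls infection the major cause of death in this population.
- **Safety data.** Section 7.4 uses pre-therapy ANC to decide whether a patient can be assessed for ANC toxicity at all. A supported value can move a patient from not evaluable to evaluable, and grading makes no allowance for G-CSF.

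**Working it through.** No figure in the plan depends on this point, so there is none to reproduce. The check is textual, followed by one proportion.

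**Step 1. Scope of the three sentences in 7a.**

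| Count | Limit set | Named in waiver | Named in support bar |
|---|---|---|---|
| Hemoglobin | yes | yes | yes |
| ANC | yes | yes | no |
| Platelets | yes | yes | yes |

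The synopsis and section 4.1 give the same result, so the omission is not a fault in text extraction.

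**Step 2. Does anything else close the gap?**

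- Exclusion 2 is a washout for cancer therapy and investigational cancer drugs. It does not cover G-CSF.
- Exclusion 16 bars unresolved Grade 2 or higher toxicity from prior therapy, but makes an exception for organ function and refers back to inclusion 7. For ANC that leads back to 7a.
- Section 5.2 permits G-CSF for acute toxicity, and section 5.3 does not prohibit it. Neither sets a pre-entry rule.
- Section 6.2.4 records prior medication over 4 weeks. It records and does not bar.
- The 7a waiver covers marrow disease only. The group admitted through the gap is therefore patients neutropenic for another reason, such as prior therapy.

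**Step 3. When does a supported screening value become the baseline?** Screening counts may be taken up to 14 days before Cycle 1 Day 1 (C1D1). Table 1, footnote 7, requires a new blood count on C1D1 unless screening was within 72 hours. SAP section 10.6.3 takes the last pre-treatment value on or before C1D1 as baseline. So the pre-therapy ANC is inflated only if:

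- (a) the G-CSF effect lasts to the C1D1 count, or
- (b) screening fell within 72 hours of C1D1 and the count was not repeated.

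Otherwise the C1D1 count shows the unsupported ANC and section 7.4 works as intended.

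**Step 4. What follows if (a) or (b) holds?** Take an illustrative unsupported ANC of 0.6 x 10^9/L.

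- Without G-CSF, 0.6 < 1 and the patient is not evaluable for ANC toxicity.
- With G-CSF lifting the value to 1 or more, the patient is evaluable. A return to 0.6 lies between 0.5 and 1, which is Grade 3 on the section 7.4 scale.
- Section 7.5.3 asks for Grade 3/4 laboratory abnormalities to be recorded as adverse events, though the investigator may leave out an isolated one without clinical significance.
- Section 7.2 makes the event related unless a clear alternative is identified.

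**Step 5. Size.** SAP section 10.6.2 counts each patient once per preferred term and divides by the safety set. SAP section 6 reports 21 enrolled. Assuming all 21 were dosed, one affected patient adds at most 1/21 = 0.048, or 4.8 percentage points, to a neutropenia rate. The documents give no number of such patients, so no total can be stated.

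**Step 6. Efficacy.** Table 6 contains no neutrophil criterion. Response classification, ORR and the two-stage rule are unaffected.

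**The case against.** The strongest reply is that the wording gap is real but its consequences need several conditions.

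- **Baseline.** A reader might infer that any G-CSF before screening gives a false baseline. The documents do not support that. The C1D1 count is normally repeated, and they give no duration for the G-CSF effect. This stands, and it is why Step 3 is conditional.
- **Attribution.** A reader might infer that every such patient adds one spurious related event. Section 7.2 allows another etiology, and known neutropenia with recent G-CSF is a plausible one. Prior medication is recorded and SAP section 10.4 lists it, so affected patients can be found. This stands, hence at most one event-bearing patient per entry.
- **Table 4.** A reader might infer that an inflated baseline distorts the recovery level for resuming treatment. It does not loosen it. Recovery is to Grade 2 or baseline, and Grade 2 begins at ANC 1. With a baseline of 0.6 the alternative would allow resumption at 0.6; a lifted baseline removes that alternative. No harm is shown on this route.
- **Narrow population.** The waiver already admits low ANC from marrow disease without a floor, and counts are repeated at C1D15, C2D1 and C2D15. This narrows the group and shortens the time a low count goes unseen. It does not close the entry gap.
- **Intent.** ANC may have been dropped by slip, or G-CSF may be a stray example. The text cannot settle which, so the request should be to reconcile the sentences and not to impose a rule.

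None of this removes the contradiction in 7a.

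**Conclusion.** The point holds as a defect in an eligibility rule. Followed as written, 7a lets the ANC limit be met on recent G-CSF by a patient whose neutropenia is not due to marrow infiltration, and no other provision prevents it. The effect on the safety data is conditional and bounded at one patient, 4.8 points on 21, for each such entry.

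It rests on these assumptions: the G-CSF effect reaches the pre-therapy count by one of the two routes in Step 3; ANC later falls below 1 for a reason other than the drug; the investigator records the event and calls it related; section 7.4 is the rule applied when the event is graded (the SAP does not repeat its evaluability clause); and all 21 enrolled patients are in the safety set.

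The documents do not show that any such patient entered, and safety is reported descriptively. They do not support a claim that the neutropenia rate is in fact biased, or any figure for several patients together. It is worth correcting because it touches patient safety and costs almost nothing.

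**What to change.** **Protocol.** In the synopsis and in section 4.1, reconcile the list of limits, the waiver sentence and the support sentence of inclusion 7a, so that the bar naming G-CSF and the ANC limit agree. The sponsor should state whether ANC falls under the existing 3-week bar. The choice is the sponsor's. The cost is one sentence in two places. If ANC is covered, some patients recently given G-CSF would have to wait or enter under the waiver.

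**Reporting.** SAP section 5.1 says the study closed after Stage 1, so rewording cannot change who entered. For this study the useful step is to take the prior-medication record, flag any patient with G-CSF within 3 weeks before the qualifying ANC, and mark that patient in the neutropenia tables and listings. No new data collection is needed, with one caution. If the 4-week record is counted back from C1D1 and the qualifying ANC was drawn 14 days before, 14 + 21 = 35 days are needed and only 28 are recorded. For those patients, check source records for the missing 7 days. If no patient is flagged, one sentence in the study report closes the matter.
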